### 8.3. Exploratory Objectives for Medical Chart Review

- 9. The abstracted medical chart data gathered for a subset of patients in the claims database analysis will be used to:
  - Identify new confounders not available in the claims such vital statistics (e.g., weight, smoking status) and inpatient treatment (e.g., ADP-ri, aspirin dose, CABG, type and number of stents, number of vessels)
  - Confirm the accuracy of the measured confounders in the claims including medical histories (in particular, history of TIA and stroke) and prior procedures
  - Compare the ADP-ri treatment administered during the index hospitalization to the first ADP-ri therapy identified post-discharge in the claims
  - Validate the claims-based major/severe bleeding algorithm
- 10. To compare stent thrombosis-related health care resource utilization through 1) three months and 2) one year post-discharge from the index hospitalization.

# 9. Research Methods

### 9.1. Study design

### 9.1.1. Study Overview

This will be a retrospective claims database analysis of medical data, pharmacy data, enrollment information supplemented with abstracted medical chart data for a subset of patients. This study will include data between 01 September 2008 and 31 August 2013. Study subjects will include health plan enrollees with evidence of a fill for prasugrel or clopidogrel within 30 days post-discharge from an ACS-PCI hospitalization and no prior TIA or stroke. The primary population was selected as guided by the US prescribing information for prasugrel in which patients with a history of TIA or stroke are contraindicated. Of note, other patients contraindicated for prasugrel, such as those with active pathological bleeding or hypersensitivity to prasugrel or one of its components, cannot be identified in this database.

## 9.1.2. Claims Database Sample

### 9.1.2.1. Inclusion Criteria

The primary and secondary objectives for the study will be addressed with commercial and Medicare Advantage health plan enrollees who meet all of the following inclusion criteria and none of the exclusion criteria below:

- ACS-PCI Hospitalization: At least one inpatient (IP) hospitalization with primary or secondary ACS diagnosis codes *and* PCI or coronary stent procedure codes between 01 September 2009 and 31 May 2013 (selection window). Note:
  - The *index admission date* will be defined as the admission date of the first such ACS-PCI hospitalization.
  - Both the index admission and discharge dates must occur during the selection window.
  - The *study index date* will be defined as the discharge date of the first such ACS-PCI hospitalization.
- **ADP-ri Index Fill**: At least one outpatient pharmacy fill for prasugrel or clopidogrel between the study index date and 30 days post-discharge from the index hospitalization. Note:
  - The *index therapy fill date* will be defined as the date of the first such fill.
  - The ADP-ri filled on the index therapy fill date will be defined as the *post- discharge index therapy*.
- Age: Aged  $\geq 18$  years as of the study index date.

<sup>13 Effient [package insert]. Indianapolis, IN: Eli Lilly and Company; 2013.

<sup>14 Prasugrel was approved by the FDA in July 2009.

• **Continuous Enrollment**: Continuously enrolled in a commercial or Medicare Advantage health plan with medical and pharmacy benefits for 12 months before the index admission date (baseline) and for at least 3 months after the index hospitalization discharge date (i.e., the study index date) or until death, if sooner (follow-up).

### **9.1.2.2**. *Exclusion Criteria*

- **Multiple ADP-ri**: Pharmacy fills for more than one ADP-ri (prasugrel, clopidogrel, ticagrelor, ticlopidine) within 30 days following the index discharge date.
- Any history of TIA or stroke: Any medical claims for TIA or stroke prior to or during index hospitalization

## 9.1.3. Cohort Assignment

Subjects will be assigned to one of two mutually exclusive cohorts based on the postdischarge index therapy (prasugrel or clopidogrel).

### 9.1.4. Study Timeframe

Five observation periods will be defined:

- 1. **Index hospitalization period**: Days between, and including, the admission and discharge dates of the index hospitalization.
- 2. **Baseline period**: 12 months before the index hospitalization admission date.
- 3. **ADP-ri index selection period**: Study index date to 30 days post-discharge from the index hospitalization.
- 4. **Variable follow-up period**: Days on and after the study index date until 3 or more months after the study index date or until death, if sooner. Maximum follow-up will be 12 months.
- 5. **Fixed follow-up period**: Days on and after the study index date until 12 months after the study index period or until death, if sooner. This one year follow-up period will be used to assess the primary endpoint as a secondary objective, adherence, persistence, and costs.

Figure 1 illustrates the study timeframe.

Figure 1. Study Timeframe

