#### Selection Window

Timeframe for identifying the index hospitalization: 01 September 2009 to 31 May 2013.

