These counts are for informational purposes only and may not represent the actual number of enrollees available for analysis. Application of other selection criteria required for this study or other factors may further reduce the available sample size. However, for the primary population, ACS-PCI patients with no history of TIA or stroke, treated with prasugrel or clopidogrel post-discharge from the index hospitalization (Table 2), the above sample sizes will provide 92% power at a 0.05 two-sided significance level to detect a 15% reduction in the adjusted hazard ratio (HR=0.85), assuming a clopidogrel base rate of 12% for MACE up to one year after the index hospitalization discharge and a 3:1 clopidogrel to prasugrel ratio. Of note, the study power

will vary as a function of both the clopidogrel event rates (as shown in Figure 2) and the magnitude of the treatment effect.

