### 9.6.5. Propensity-Adjusted Outcomes Analyses

### 9.6.5.1. Analysis of Categorical Outcomes

Categorical outcomes variables associated with the secondary objectives including rates of rehospitalization (disease-related and all-cause), bleeding, switching, discontinuation, and all-cause mortality may be assessed as follows: If propensity score matching method is implemented, the correlation for paired sample will be considered in the statistical methods. However if propensity score stratification method is implemented, PROC GENMOD model controlling the propensity score strata may be applied. The interaction between propensity score strata and the treatment will also be examined. If the interaction term turns out to be significant, the relative risk in each stratum will be outputted to examine the variability across the strata.

Cohort differences will be summarized using both the estimated relative risk and risk differences from this model. The number needed to treat (NNT) and number needed to harm (NNH) will be defined as the inverse of the risk difference (1/risk difference).

 <sup>26 Austin PC, Grootendorst P, Anderson GM. A comparison of the ability of different propensity score models to balance measured variables between treated and untreated subjects: A Monte Carlo study. *Statistics in Medicine*. 2007;26:734–753. doi: 10.1002/sim.2580
  Austin PC, Mamdani MM. A comparison of propensity score methods: A case-study estimating the effectiveness

<sup>27 Austin PC, Mamdani MM. A comparison of propensity score methods: A case-study estimating the effectiveness of post-AMI statin use. *Statistics in Medicine*. 2006;25:2084–2106. doi: 10.1002/sim.2328

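### The fixed 12-month period keeps deaths but in effect loses survivors without a full year of data, and the one-year RR, RD and NNT/NNH name no censoring; secondary absolute risks would be off

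*Protocol*

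**What the plan says.** Three dates and definitions in the protocol interact.

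- Section 9.1.1: "This study will include data between 01 September 2008 and 31 August 2013".
- Section 3, Selection Window: index hospitalizations are identified from "01 September 2009 to 31 May 2013". Section 9.1.2.1 requires admission and discharge to fall inside that window.
- Section 9.1.4: the fixed follow-up period covers "Days on and after the study index date until 12 months after the study index period or until death, if sooner". It serves adherence, persistence, costs and the secondary assessment of the primary endpoint, which section 9.6.5.2 describes as assignment to the first treatment filled, regardless of switching or stopping.

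Entry to the study as a whole needs continuous enrolment "for at least 3 months after the index hospitalization discharge date (i.e., the study index date) or until death, if sooner". The variable follow-up period therefore lasts 3 to 12 months, or until death. Section 9.3.2 adds that patients who left the plan because they died may be kept despite short enrolment. Section 9.6.6, item 3(h), lists patients with under 12 months of enrolment as an optional sensitivity analysis.

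Section 9.6.5.1 covers rehospitalization, bleeding, switching, discontinuation and all-cause mortality as categorical outcomes: "Cohort differences will be summarized using both the estimated relative risk and risk differences from this model". NNT and NNH are the inverse of the risk difference. No censoring rule, person-time or follow-up period is named there.

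**The concern.** Two separate problems arise, and they run in opposite directions.

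**Fixed period.** A patient discharged after 31 August 2012 cannot be followed alive for 12 months before the data end, but can complete the period by dying. The same asymmetry applies to disenrolment at any calendar time: a survivor who leaves the plan fails the 12-month requirement, while a patient who dies while enrolled meets it. Membership then depends on the outcome, and death is a MACE component. A Cox model fitted inside this cohort does not undo the selection. This matters because the first-treatment analysis is the natural check on the on-treatment primary analysis, which censors at switching and discontinuation.

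**Categorical one-year outcomes.** These are not assigned to the fixed period, so they fall to follow-up of 3 to 12 months. A simple proportion counts a patient seen event-free for 3 months as a one-year non-event. Absolute risks and risk differences then come out too small, and NNT and NNH too large.

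**Working it through.** **The plan's own figure.** Section 9.4 states that the sample "will provide 92% power at a 0.05 two-sided significance level to detect a 15% reduction in the adjusted hazard ratio (HR=0.85". The other inputs given there are a 12% one-year MACE risk on clopidogrel and three clopidogrel patients for each prasugrel patient. Take 5,101 prasugrel patients (Table 2) and 3 × 5,101 = 15,303 clopidogrel patients.

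- Prasugrel risk: 1 − 0.88^0.85 = 10.3%.
- Events: 5,101 × 0.103 + 15,303 × 0.12 ≈ 2,362.
- Schoenfeld power: Φ(√(2,362 × 0.25 × 0.75) × |ln 0.85| − 1.96) = 92.8%. A two-proportion calculation gives 91.6%.

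The stated 92% reproduces, so the 12% risk and HR 0.85 are used below.

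**Share of the window that cannot give 12 months.** 1 September 2009 to 31 May 2013 is 1,369 days. 1 September 2012 to 31 May 2013 is 273 days. 273/1,369 = 19.9%.

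**Model.** Event times are exponential and entry is even over the window. Let G(t) be the probability of still being observable at time t. G is 1 up to month 3; it then falls as (1 − 0.2u) × (1 − d)^u, where u runs from 0 at month 3 to 1 at month 12, and d is the disenrolment proportion over those months. The protocol gives no value for d or for mortality. Assumed: d = 0, 15% or 25%, and one-year mortality of 3%.

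**Fixed cohort.** Observed deaths D = ∫ f(t)G(t)dt, with f the density of death times. Retained survivors = 0.97 × G(12). Mortality reads D / (D + 0.97 G(12)). For MACE, take 12% made up of 3% deaths and 9% survivors with a non-fatal event; only deaths escape the 12-month requirement, so MACE reads (D + 0.09 G(12)) / (D + 0.97 G(12)).

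| d | G(12) | D | Mortality reads | MACE reads |
|---|---|---|---|---|
| 0 | 0.80 | 0.0278 | 0.0278/0.8038 = 3.45% (+15%) | 12.4% (+3%) |
| 15% | 0.68 | 0.0263 | 0.0263/0.6859 = 3.83% (+28%) | 12.75% (+6%) |
| 25% | 0.60 | 0.0252 | 0.0252/0.6072 = 4.15% (+39%) | 13.05% (+9%) |

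**Crude one-year proportions over 3 to 12 months.** The crude proportion is ∫ f(t)G(t)dt. The 12% risk serves only as an illustration, because section 9.6.5.1 does not list MACE. True values: 12.0% against 10.3%, RD 1.70 points, NNT 59, RR 0.858.

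| d | Comparator reads | RD (points) | NNT | RR |
|---|---|---|---|---|
| 0 | 11.1% | 1.58 | 63 | 0.858 |
| 15% | 10.55% | 1.50 | 67 | 0.857 |
| 25% | 10.1% | 1.45 | 69 | 0.857 |

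**Unequal follow-up, no true effect.** Suppose one cohort has 15% late entry and 15% disenrolment, and the other 25% and 25%. With 3% mortality in both, the fixed cohort reads 3.68% against 4.34%, RR 1.18. Crude proportions give an RR of about 0.93. These splits are assumed; nothing in the protocol shows them.

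**The case against.** The strongest reply is that the fixed cohort is inferred. Section 9.1.4 defines an observation period, the only enrolment criterion is 3 months, and no sentence says that survivors without 12 months are removed. The abstract also leaves study timeframes to the SAP. It is true that this is not stated. But if such survivors stay in, the fixed period is the same as the variable one and has no purpose. Section 9.6.6 item 3(h) and section 9.3.2 point the same way.

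Section 9.6.5.1 is partly permissive about method and silent on censoring, so the SAP could settle that half. However, it commits to reporting relative risks, risk differences and their inverse.

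Several limits stand in full:

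- Kaplan-Meier curves and Cox models are planned for MACE and all-cause mortality, and Cox models for NACE (sections 9.6.3 and 9.6.5.2).
- The 30-day and 3-month horizons are observed in full for every eligible survivor.
- Table 1 specifies costs and utilization per patient per month, which scales for unequal follow-up time, though it does not change who is included.
- Index year is a listed baseline variable and can enter the propensity score.

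A reader might infer that the primary result is biased too, because the 3-month entry rule has the same exemption for death. The data cut-off does no harm there, since the last discharges still have three months before 31 August 2013. Only disenrolment in the first three months could matter, and the protocol gives no rate for it. A reader might also infer a biased treatment comparison. With equal follow-up in both cohorts, the RR stays at 0.857 to 0.858.

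**Conclusion.** The point holds for secondary analyses and mainly for absolute risks. On the natural reading, the fixed cohort overstates one-year mortality by about 15% to 39% in relative terms, and MACE by about 3% to 9%. Crude one-year proportions understate risk by about 7% to 16% and move an NNT of 59 to 63 to 69. The 20% late share follows from the protocol's dates if entry is even; 3% mortality and 0 to 25% disenrolment are assumptions.

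The errors belong to different analyses and have opposite signs, so it would be wrong to say that all one-year risks are biased in one direction. Relative effects are at risk only if calendar time or disenrolment differs by cohort. That is possible, because generic clopidogrel was released in May 2012 and every late discharge follows it, but it is not shown. The primary on-treatment Cox analysis, the Kaplan-Meier and Cox analyses on variable follow-up, and the 30-day and 3-month results are not affected by these two points. This should be fixed before outcome analysis; it does not threaten the primary objective.

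**What to change.** 1. Run the first-treatment MACE analysis in all eligible patients, censoring at disenrolment or 31 August 2013, and do not require 12 months of enrolment.
2. Take one-year risks, RR, RD and NNT/NNH from Kaplan-Meier estimates for death, MACE and NACE, and from cumulative incidence with death as a competing event for bleeding, rehospitalization, discontinuation and switching. Use bootstrap intervals.
3. Where a full 12-month window is needed (proportion of days covered, costs), restrict to discharges on or before 31 August 2012 for all patients, deaths included, and handle disenrolment by censoring or weighting.
4. State in section 9.1.4 what happens to survivors with less than 12 months of data.

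The cost is protocol or SAP wording and modest programming, with no new data. The full-year adherence and cost cohort loses about the last 9 of 45 selection months. Removing the 3-month entry rule would be a larger redesign than this defect needs.

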### 9.1.5. ACS-PCI with No Prior TIA or Stroke Subgroups

Baseline characteristics and clinical and economic outcomes between prasugrel and clopidogrel patients will be examined for the following subgroups:

- 1. <75 years of age OR  $\geq$ 75 years of age with prior MI or diabetes\*
- 2. Index admission diagnosis (STEMI, NSTEMI, UA)
- 3. Gender (Male vs. Female)

\* Subgroup #1 was selected to reflect the US prescribing information for prasugrel in which patients with a history of TIA or stroke are contraindicated, and patients  $\geq$ 75 years of age are generally not recommended for prasugrel use, except in high-risk situations, such as patients with diabetes or a history of prior MI.

### 9.1.6. Medical Chart Review Sample

The objectives for the medical chart review as described in Section 8.3 will be addressed by abstracting medical chart data for a subset of ACS-PCI patients with no evidence of TIA or stroke in the claims during baseline or the index hospitalization. In addition, the medical chart sample will be limited to commercial health plan enrollees, as medical chart abstraction is not allowed by Federal law for Medicare Advantage health plan enrollees. An oversample of 3,600 study subjects in the claims database analysis will be identified in order to obtain a final sample of 1,200 completed charts, or 600 per cohort. The hospital or medical facility where each index ACS-PCI hospitalization took place will be identified and contacted to arrange medical chart review. The final sample will be a convenience sample of commercial study subjects with facilities willing to participate in the medical chart abstraction process. True

representativeness cannot be guaranteed due to the voluntary nature of the chart review process. Abstracted medical chart data will be linked to the administrative claims data for analysis.

### 9.2. Variables

Table 1. Study Variables by Study Objectives and Data Source

OBJECTIVE	VARIABLE	DEFINITION	CLAIMS	CHART
1, 4, 5, 10	Index	Bleeding during the index hospitalization (n, %)	Y*	Y
	hospitalization	- Any bleeding		
	bleeding	- Any transfusion of WB, PRBC, or platelets		
		- Major/severe (*claims algorithm)	N	X
	Index	- Periprocedural (24-48 hours after PCI)	N	Y
	hospitalization stroke	Any evidence of a stroke occurring during the index hospitalization on the medical chart $(n, \%)$	N	Ŷ
	Post-discharge bleeding	Transfusion or intracranial hemorrhage bleeding during 30 days, 3 months and 1 year post-discharge from the index hospitalization (n, %)	Y	N
		Major/severe bleed (*algorithm)	Y*	N
		Days to first bleed (mean, SD, median)	Y	N
	Post-discharge disease-related events	Evidence of other CV events such as MI, revascularization, stroke, unstable and stable angina, and congestive heart failure during 1 year post-discharge from the index hospitalization (n, %)	Y	N
	MACE	and 1 year post-discharge from the index hospitalization (n, %):		
		- All-cause mortality	Y	N
		- Hospitalization for MI (NSTEMI, STEMI)	Y	N
		- Hospitalization for unstable angina (UA)	Y	N
		
 
Hospitalization for stroke
 
	Y	N
		- Revascularization (PCI, CABG)	Y	N
	D . 1. 1	Days to the first occurrence of each event (mean, SD, median)	Y	N
	Post-discharge NACE	MACE or evidence of hospitalization for bleeding during 30 days, 3 months and 1 year post-discharge from the index hospitalization (n, %)	Y	Ν
	Post-discharge other Composite	Composite of all-cause mortality, hospitalization for stroke, or rehospitalization for MI $(n, \%)$	Y	N
	Post-discharge stent thrombosis	Stent thrombosis (*algorithm)	Y*	N
2	Age	As of the study index date (n, %, mean, SD, median years) - 18-44, 45-54, 55-64, 65-74, ≥75	Y	N
	Comorbidities/ Medical history	
 
Baseline comorbidities (n, %)
 
Arterial embolism, Asthma, Atrial fibrillation, Cardiac dysrhythmia, Cardiomyopathy, Cerebrovascular disease, Chronic Obstructive Pulmonary Disease (COPD), Deep venous thrombosis, Diabetes, Dyslipidemia, Dyspnea, Congestive Heart Failure (CHF), Hemorrhagic tendencies of blood dyscrasia, History of bleeding, Hypertension, Hypotension, Ischemic Heart Disease, other than ACS (MI or UA), TIA, Liver disease, Obesity, Osteoarthritis, Peripheral vascular disease, Phlebitis, Pulmonary embolism, Renal impairment (Renal failure, Chronic Kidney Disease (CKD), Other renal insufficiency), Rheumatoid Arthritis, Sepsis, Stroke (Hemorrhagic stroke, Ischemic stroke, Unspecified stroke), Thyrotoxicosis, thrombocytopenia, peptic ulcer disease (n, %)
 
Quan-Charlson Comorbidity Index (n, %, mean, SD, median)
 
0-1, 2, 3, 4+
 
	Y	Y
	Health care	All-cause medical encounters during baseline (n, %, mean, SD, median)	Y	N
		
 
Inpatient admissions
 
Length of inpatient stays
 
		

OBJECTIVE	VARIABLE	DEFINITION	CLAIMS	CHART
		
 
Outpatient visits (physician and outpatient hospital visits)
 
Other medical encounters
 
		
	Health care	All-cause costs during baseline (mean, SD, median)	Y	N
	resource costs	- Total (medical + pharmacy costs)	_	
		- Medical costs		
		- Inpatient costs		
		- Emergency department costs		
		- Outpatient costs		
		- Pharmacy costs		
	Health plan region	US Census geographic regions (n, %) - Northeast, Midwest, South, West	Y	Ν
	Index year	Year of the index hospitalization admission date	Y	Y
	Insurance type	Commercial, Medicare Advantage (n, %)	Y	N
	Primary payer type	HMO, PPO, POS, Other (n, %)	Y	N
	Prior MI	Yes, No (n, %)	Y	Y
	Prior	CABG, PCI (n. %)	Y	Y
	revascularization		_	
	Sex	Male, Female (n. %)	Y	Y
	Smoking status	Yes. No (n. %)	Ν	Y
	Socioeconomic	Race/ethnicity (n. %)	Y	Y
	status (SES)	- Caucasian, African American, Hispanic, Asian, Other		
	()	Income/Net worth (mean, SD, median)	Y	N
	Treatment	Baseline medication use (n. %)	Y	N
	utilization	- ADP-ri (clopidogrel, prasugrel, ticagrelor, ticlopidine).	_	
		phosphodiesterase inhibitor (cilostazol). HMG CoA		
		reductase inhibitors (statins), proton pump inhibitors.		
		antihypertensives (major class), antidiabetes medications		
		(major class)		
	Weight	Lbs/kg (mean, SD, median)	Y	Y

6, 7	Post-discharge resource utilization	PPPM number of all-cause and disease-related health care         utilization during one year post-discharge from the index         hospitalization (n, %, mean, SD, median)         - Inpatient admissions         - Length of stays         - ICU/CCU stays         - Length of ICU/CCU stays         - Outpatient hospital visits         - Physician office visits         - Family/general practice         - Cardiology         - Endocrinology         - Other specialties         - Emergency department visits	Y	Ν
	Post-discharge resource costs	PPPM all-cause and disease-related costs (mean, SD, median)         during one year post-discharge from the index hospitalization:         -       Total (medical + pharmacy costs)         -       Medical costs         -       Inpatient costs         -       Emergency department costs         -       Outpatient hospital costs         -       Physician office visits         -       Family/general practice         -       Cardiology         -       Endocrinology         -       Other specialties         -       Other medical encounters         -       Pharmacy costs	Y	N
10	Index	PCI procedure during the index hospitalization (n, %)	Y	Y
(See Medical Chart Abstraction Form for complete list of	hospitalization revascularization	Stent implantation (n, %) - DES, BMS, unknown, none	Y	Y
		- 1, 2, 3, 4+ Number of vessels (n, %)	Y	Y
index		- 1, 2, 3, 4+		
variables)		CABG during the index hospitalization (n, %)	Y N	Y
		admission (mean, SD, median)	IN	Ŷ
	Index hospitalization	ACS diagnosis during the index hospitalization (n, %) - STEMI, NSTEMI, UA	Y	Y
		Days during index hospitalization (mean, SD; median)	Y	Y
		Days during ICU/CCU index hospitalization (mean, SD; median)	N NI	Y
		and PCI (mean, SD, median) Initial and discharge dose amounts of prasugrel and clopidogrel	N N	Y Y
		% with loading dose Hospital characteristics (n. %, mean, SD, median)	Y	N

OBJECTIVE	VARIABLE	DEFINITION	CLAIMS	CHART
		- urban/rural		
		Medications administered during the index hospitalization (n, %)	N	Y
		
 
ADP-ri, aspirin, glycoprotein IIb/IIIa inhibitors
 
		
		(abciximab, eptifibatide, tirofiban), fibrinolytic therapy,		
		anticoagulant (unfractionated heparin, LMWH		
		(dalteparin, enoxaparin, tinzaparin), fondaparinux), direct		
		thrombin inhibitor (bivalirudin), other anticoagulant or		
		antithrombin (rivaroxaban, dibigatran, apixaban,		
		coumadin)		
		- Persistence with initial inpatient therapy on the discharge	N	Y
		date		

